12.0 Objectives and Rationale

12.1 * Overview

Briefly state the **purpose of this study**. Give enough background and rationale to provide both scientists and lay members of the IRB and ACCTS with the basis for exposing human subjects to the risks involved.

Obesity increases the risk for the development of and the progression to metastasis of numerous malignancies including hormone receptor-positive breast cancer in postmenopausal women (1). Medications that suppress the biosynthesis of estrogen or block its actions decrease the risk of hormone receptor-positive breast cancer (2). In obese women, inflammation manifested as crown-like structures (CLS), is associated with NF- κ B-dependent induction of proinflammatory mediators including TNF- α , IL-1 β , IL-6 and COX-2-derived PGE₂ in breast white adipose tissue (3). Moreover, increased levels of aromatase, the rate-limiting enzyme for estrogen synthesis, are found in association with elevated levels of proinflammatory mediators in breast white adipose tissue (4). This finding is consistent with extensive evidence that proinflammatory mediators, including PGE₂, induce aromatase expression (5-6). Importantly, we have evidence that it is common for inflammation to occur in both breast and abdominal subcutaneous white adipose tissue, in parallel, in obese women making abdominal subcutaneous white adipose tissue a useful surrogate tissue to study.

If reductions in subcutaneous adipose tissues of the inflammatory markers to be studied and aromatase levels directly correlate with reduced urinary excretion of PGE-M, an index of prostaglandin activity in the body, then this will support direct effects of Celecoxib upon adipose tissue inflammation as a mechanism and also will underlie the use of urinary PGE-M determinations as a biomarker reflecting changes in adipose tissue inflammation.

The potential use of celecoxib in modulating aromatase activity is supported by epidemiologic evidence that chronic use of nonsteroidal anti-inflammatory drugs (NSAIDs), prototypic inhibitors of PGE₂ synthesis, decrease levels of circulating estrogens and reduce the risk of breast cancer (7). In addition, increasing numbers of studies have suggested that other complications of obesity including cardiovascular disease and type 2 diabetes mellitus are related to inflammatory activity in adipose tissue.

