We plan to study circulating levels of estradiol and estrogen metabolites and the urinary excretion of estrogen metabolites to establish whether this dose of celecoxib, by reducing aromatase, actually alters estrogen metabolism as hypothesized if adipose tissue inflammation is reduced. Direct demonstration of such a change in estradiol and estrogen metabolism should point to the importance of reducing adipose tissue inflammation in obese post-menopausal women in order to reduce the risk and the spread of estrogen receptor positive breast cancer in such patients.

Obesity is associated with elevated levels of urinary PGE-M, a biomarker that reflects increased systemic levels of PGE₂. We hypothesize that treatment with celecoxib, a selective COX-2 inhibitor, will reduce levels of PGE₂ and aromatase in inflamed abdominal subcutaneous white adipose tissue of obese postmenopausal women. This concept is supported by preclinical evidence that celecoxib suppressed PGE₂ levels and aromatase activity in the mammary glands of obese mice (Fig. 1). Celecoxib also suppressed the elevated levels of urinary PGE-M found in obese mice (Fig. 2). Based on this constellation of findings, we speculate that celecoxib-mediated decreases in levels of urinary PGE-M will correlate with reduced levels of PGE₂ and aromatase expression in abdominal subcutaneous white adipose tissue of obese postmenopausal women. Celecoxib is the preferred agent for these studies because it does not have the anti-platelet activity that traditional NSAIDs possess. Hence, biopsies of abdominal subcutaneous white adipose tissue can be done without a medication-related increased risk of bleeding.

The results of this study could be important for highlighting the potential benefit of NSAIDs for reducing the risk of hormone receptor-positive breast cancer in obese postmenopausal women, a growing segment of the population.

Significance

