The use of NSAIDs has been associated with a reduced risk and spread of colorectal cancer. Most epidemiological studies suggest that use of NSAIDs also is associated with a reduced risk and spread of breast cancer although the protective effects are more modest. We speculate that this class of medication like others will be effective in some but not all individuals to reduce breast cancer risk. In particular, we hypothesize that these agents will be of benefit if used chronically in the up to 75% of obese postmenopausal women who demonstrate white adipose tissue inflammation and CLS. If Celecoxib suppresses levels of inflammation and aromatase in abdominal white adipose tissue which is likely to mirror what occurs in breast white adipose tissue, this would suggest that chronic use of NSAIDs is likely to reduce the risk and spread of hormone receptor-positive breast cancer in this growing segment of the population. Importantly, if reduction in urinary PGE-M reflects reduction in adipose tissue inflammation this would be a useful non-invasive marker for this property in future studies.

We additionally plan to study the fecal microbiota of 5 of the 10 participants being studied.

Studies on metabolic diseases such as obesity during the past few years have included important consideration of the impact of changes in the colonic microbiome. Indeed, several of our recent studies at The Rockefeller University Hospital have included a collection and storage of fecal specimens for later analysis. We, in collaboration with [name] at Cornell have established a relationship with [name] at MSKCC who is willing to perform analysis on specimens that were collected immediately before and after 10% weight loss in obese volunteers (PHO 785).

Our metabolic studies usually have been performed in small groups of subjects who are studied while consuming a preselected diet before and after an intervention.

As we plan similar studies, it has become evident that we do not know how soon after admission to RU and initiating a Bionutrition Department provided diet should fecal specimen collection be initiated as a stable baseline before starting the intervention. Previously, we only have used 3 days before the intervention based on scant data in the literature. We now believe that it is very important to determine how long it takes under the condition of our studies at RUH to establish reasonable fecal microbiota stability.

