Available information suggests that there are 3 predominant microbe enterotypes described initially in 2011 (20). Studies in 5 subjects consuming either a high fat/low fiber or a low fat/high fiber diet in a single study suggested that the distinct differences between individual subjects generally were maintained over 10 days after an abrupt change in the 1st 24 hours. No switching in the primary 3 enterotypes was detected within 1 week of the diets (21).

In a study of Malawi twins, discordant for kwashiorkor, administration of a therapeutic food supplement resulted in modest but non significant changes in the fecal microbiota in 2 weeks (22).

A much quoted study by Faith et al evaluated the stability of the fecal microbiome up to 5 years showing that up to 60% of the individual species remained stable (23). However, weight loss impaired microbiota stability in studies performed before and after 8 weeks of a low calorie diet.

In our present studies, we had taken fecal samples 2-3 days after the RUH admission and the start of a diet designed by our Bionutrition Department that mimicked each subject's pre-study diet and then initiated the intervention. However, on the basis of the available information, we do not know how long to administer such a diet before taking the initial fecal sample prior to the medical intervention such as Celecoxib. The present proposed study will determine whether the fecal microbiota is stable after 3 or 7 days or needs 14 or more days. This information will guide our procedures in future similar studies.

12.2 * Engaging Stakeholders: Describe any plans to engage other stakeholders (Scientists, practitioners, patients, advocacy groups, etc.) for hypothesis generation, or feasibility purposes.

[name] who will perform several analyses of adipose tissue pertaining to effects of Celecoxib on the aromatase enzyme. [name] and [name] who will perform microbiome studies that aim to determine whether Celecoxib alters fecal microbiota composition and whether a self-selected diet mimicking a subject's pre-study long-term diet will keep fecal microbiota composition constant.

12.3 * Hypothesis

Describe the **research hypothesis** in a single sentence.

Celecoxib, an inhibitor of cyclooxygenase-2 (COX-2) will reduce urinary excretion of PGE-M, and suppress levels of prostaglandin E₂ (PGE₂) and aromatase in inflamed abdominal subcutaneous adipose tissue in grade 2-3 obese postmenopausal women.

12.4 * Aim(s)

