Indicate how you will **address the hypothesis** (e.g., to compare groups, to estimate a parameter, to ascertain feasibility). Since the sample size determination is usually based on the primary aim only, the primary aim should be sufficient to justify the study.

To determine whether oral administration of celecoxib 200 mg BID to grade 2-3 obese postmenopausal women will significantly reduce the excretion of PGE-M in the urine.

12.5 * Primary Outcome(s)

Indicate which **variable(s)** will be assessed to judge the primary specific aim. Give measurement units, if applicable.

PGE-M in urine will be significantly reduced

12.6 * Secondary Outcome(s)

Indicate which **additional variable(s)** will be assessed to judge the secondary outcome(s). Give measurement units, if applicable.

Crown-like structures in subcutaneous adipose tissue

PGE₂ in subcutaneous adipose tissue

aromatase in subcutaneous adipose tissue biopsies and crown-like structures in subcutaneous adipose tissue

Circulating levels of TNF- α , IL-6, IL-8, and MCP-1.

Levels of circulating serum estradiol and selected estrogen metabolites in serum and urine

Determination of the length of time to achieve stability of fecal microbiota

Serum endocannabinoid concentration at baseline (Days 3 and 14) , Day 13 & 24, and Outpatient End of study visit

12.7 * Methods and Procedures

Please provide a description of the laboratory and clinical analyses and procedures that will be performed. Include the role of external collaborators and consultants when appropriate.

This is a pilot study of 10 grade 2-3 (BMI between 35-50) obese postmenopausal women to determine if treatment with Celecoxib 200 mg bid for 10+-1 days leads to reduced levels of abdominal subcutaneous white adipose tissue PGE₂, and aromatase activity in association with decreased levels of urinary PGE-

M. Previous studies (17) have shown that this interval is sufficient to achieve steady state circulating levels of the drug and to significantly suppress urinary PGE-M levels.

Two screening visits will take place in the OPRC and the remainder of the study will be an in-patient study in which the participants may leave RUH for periods of time during the day, unless it is a "testing" day.

Patients will be given a 3-day rotating diet based on their regular diet as reported and reviewed with the bionutrition department.

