The sequence data will be screened and filtered using Mothur before each sequence is classified using a modified inhouse database containing sequences from GreenGenes 99 and retrieved 16S sequences from Genbank. The relative abundance of the microbiota will be represented by the percentages of the classified taxa sequences out of the total sequences present in the sample. In addition to the classification of the raw sequences, sequences that fall into an operation taxonomic unit (OTU) with 97% similarity will also be classified.

Additionally, the biodiversity of the microbiota of a sample will be surveyed using the Shannon Diversity Index. The comparison of the biodiversity between samples will be measured by unweighted UNIFRAC distances and visually represented by the Principal Components Analysis. A LDA Effect Size (LEfSe) analysis can be completed to look for specific bacteria that may contribute to any differences seen between groups of samples.

12.8 * Data Analysis

Describe method(s) of data analysis. Include the role of external collaborators as appropriate.

With 10 subjects, we will be able to detect effect sizes larger than 1 with 80% power at 0.05 significance level on a 2-tail test

12.9 * Explain the rationale for the choice of statistical measures and the number of subjects proposed for the study, including the power calculations when applicable.

In a study including women across the BMI spectrum, the effect size for the pre vs post differences in PGE-M excretion was found to be 0.64 for current smokers, 1.06 for former smokers and 0.68 for non-smokers (17).

Mice data shows that baseline levels of PGE-M are twice as high in obese than lean mice and the reduction on PGE-M is 70% higher in obese mice. Based on this, we will power our study to detect an effect size of 1 in the decrease of PGE-M levels with treatment. Studies in obese mice have shown an almost 3-fold increase in excretion of PGE-M compared to lean mice ([name] unpublished observations).

To test if the measurement of PGE-M in the urine will decrease after administration of Celecoxib 200 mg BID a paired t-test will be used.

A similar approach will be used to test the secondary outcomes including PGE-2 in adipose tissue, cytokine levels (log-transformed), and estrogen metabolites. Decrease in outcomes will be correlated to identify which variable correlates with the primary outcome.

12.10 * Will samples be coded?

Yes No

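### Should tissue PGE2 and aromatase be analysed separately in CLS-positive women because the hypothesis is stated for inflamed fat?

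*Combined protocol and SAP*

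**What the plan says.** The hypothesis in 12.3 names PGE2 and "aromatase in inflamed abdominal subcutaneous adipose tissue in grade 2-3 obese postmenopausal women". The Overview in 12.1 says much the same: "aromatase in inflamed abdominal subcutaneous white adipose tissue of obese postmenopausal women". It also treats CLS as the visible form of fat inflammation in obese women. Its Significance part expects long-term benefit in the "up to 75% of obese postmenopausal women who demonstrate white adipose tissue inflammation and CLS".

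The operative sections drop the qualifier:

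- 12.6 lists "aromatase in subcutaneous adipose tissue biopsies and crown-like structures in subcutaneous adipose tissue", with tissue PGE2 on a separate line.
- 12.7 asks whether treatment "leads to reduced levels of abdominal subcutaneous white adipose tissue" PGE2 and aromatase activity in 10 women with BMI 35-50.
- 12.1 itself, later in the paragraph that states the hypothesis, speaks of aromatase in abdominal fat without calling it inflamed.
- 13.11 and 13.12 contain no CLS or tissue-inflammation criterion.

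Two analyses in 12.9 reach these outcomes. One is the paired comparison: "A similar approach will be used to test the secondary outcomes including PGE-2 in adipose tissue". Aromatase is not named there but falls under the secondary outcomes. The other is a correlation: "Decrease in outcomes will be correlated to identify which variable correlates with the primary outcome". Neither uses baseline CLS.

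**The concern.** If the hypothesis is about inflamed tissue and up to a quarter or more of the women have none, the all-10 mean change mixes two kinds of tissue. Should non-inflamed fat respond less, that mean understates the effect the hypothesis names, and the test loses power. A null result could then mean either no effect in inflamed fat or an effect that was diluted. No CLS-positive definition is fixed, so any later split by CLS would be chosen with the data in view. The natural remedy is a prespecified paired estimate in CLS-positive women, reported beside the all-10 result. The pre-dose biopsy (Day 3, or Day 14 in the early-admission group) would supply the baseline reading without extra visits.

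**Working it through.** **Inputs from the plan.** n = 10, two-sided 0.05, 80% power (12.8); effect size 1 and paired t-test (12.9, set for urinary PGE-M); up to 75% with inflammation and CLS (12.1).

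**Assumptions.** The documents give no tissue effect size, no response in non-inflamed tissue, and no CLS prevalence at BMI 35-50. I take effect size 1 in inflamed tissue, prevalence p of 60%, 75% or 90%, relative response e in non-inflamed tissue from 0 to 1, and within-group SD of the change equal to 1.

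**1. The plan's own figure.** Noncentral t with 9 df and noncentrality 1 × √10 = 3.16 gives power 80.3%, which matches the stated 80%.

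**2. Are CLS-negative women likely?** The chance of at least one in 10 is 1 − p^10: 99%, 94% and 65% at p = 60%, 75% and 90%. So the question is a real one.

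**3. All-10 test under dilution.** Mean = p + (1−p)e; SD = √[1 + p(1−p)(1−e)²]. At p = 75%:

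| e | mean | mean/SD | all-10 power |
|---|---|---|---|
| 0 | 0.75 | 0.688 | 49% |
| 0.25 | 0.81 | 0.773 | 59% |
| 0.5 | 0.88 | 0.855 | 67% |
| 0.75 | 0.94 | 0.932 | 75% |
| 1 | 1.00 | 1.000 | 80% |

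**4. Power of the CLS-positive subset.** Averaged over a Binomial(10, p) count, power is 50%, 63% and 74% at p = 60%, 75% and 90%. It exceeds all-10 power only when e is below 0.32, 0.37 and 0.42 respectively.

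**5. Precision.** The 95% CI half-width is t(0.975, n−1)/√n: 2.262/√10 = 0.72 SD for all 10 and 2.447/√7 = 0.93 SD for 7 women. At 75% prevalence there is a 22% chance of 6 or fewer CLS-positive women.

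**6. Which estimate lies closer to the inflamed-tissue effect?** Bias and variance both count. At p = 75%, before any regression to the mean:

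- All 10: mean squared error = [0.25(1−e)]² + [1 + 0.1875(1−e)²]/10 = 0.1 + 0.08125(1−e)².
- Subset: the average of 1/K over the binomial count K, about 0.139.
- These are equal when (1−e)² = 0.039/0.08125 = 0.48, so e is about 0.31.

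**7. Regression to the mean.** CLS and the outcomes come from the same baseline biopsy and there is no control arm. If CLS correlates c with the transient part of the baseline reading, selecting CLS-positive women shifts the apparent fall by c × [φ(z)/p]/√2. At p = 75% this is 0.300c: 0.09 SD for c = 0.3 and 0.15 SD for c = 0.5. Simulating the model with this included, the subset has the smaller root mean squared error, and the smaller mean absolute error, only when e is below about one third, for either c. At e = 0.5 and c = 0.3, the root mean squared error is 0.356 for all 10 and 0.379 for the subset.

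**The case for a change.** The best case for a change is that the qualifier is not a stray word. It appears in both 12.1 and 12.3, and the Significance part of 12.1 separates women with inflammation and CLS from other obese women and expects the drug class to help only some. Tissue PGE2 and aromatase sit in the one-sentence hypothesis, and the breast-cancer inference in 12.1 would be drawn from them. The correlation in 12.9 does not fill the gap, because it relates changes to the change in PGE-M and not to baseline CLS. The extra estimate would cost little, and fixing its definition in advance would protect it from selective reporting.

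The reading of the text stands, and so does the caveat about a null result. The inference to a needed change does not. The 12.1 sentence about who benefits concerns long-term use and cancer risk, not the 10-day tissue response, and nowhere do the documents say that CLS-negative tissue responds little. The subset also needs a CLS cut-off that the documents do not supply, splits 10 women into roughly 7 and 3, and introduces regression to the mean. A plot of each woman's change against her baseline CLS would look at the same question with all the data and no threshold. Statisticians could fairly differ between the two, and analysts can draw that plot without a plan amendment. Finally, 13.9 projects no new consents and 14.1 no inpatient days in the next year, so collection may be over. If the tissue results have been seen, any CLS split would be post hoc in any case.

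**Conclusion.** No change follows. The hypothesis is worded more narrowly than the analysis, but the all-10 paired test is a valid test of these secondary outcomes in the women that 12.6 and 12.7 describe. It errs towards understating an inflamed-tissue effect, so a significant fall would still support 12.3. The primary aim, the sample size and the 80% power for urinary PGE-M are unaffected.

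What remains is a point of interpretation: a null all-10 result would not alone rule out an effect limited to inflamed fat. At an assumed 75% prevalence and effect size 1, all-10 power for the tissue outcomes runs from 49% if non-inflamed tissue does not respond at all to 80% if it responds equally. A CLS-positive subset does better on power only below a relative response of about 0.37, and on accuracy only below about one third. Nothing in the documents places the response that low. The prevalence, the tissue effect size, the relative response and the correlation behind the regression to the mean are all assumptions, and the calculations also assume that one biopsy classifies CLS without error. Removing the word for inflamed from the hypothesis would tidy the text but alter no analysis.

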5 out of the 10 participants recruited will be asked to be admitted to the Rockefeller University Hospital IPU 11 days earlier (2 weeks prior to Celecoxib administration) for a total of 24 inpatient days in order to determine stabilization time for fecal microbiota. 4 additional stool samples will be collected at Days 0,3, 7, and 11, +/- 1 day.

Screening Visit #1

Informed consent

Medical History and Physical exam

EKG

Waist measurement

Distribution of 3-day food diary

HIV POCT

Subjects will be instructed to fast 10 hours prior to their next visit for fasting labs.

Subjects will be instructed to discontinue taking over the counter medications (OTCs). Those subjects which require medication for relief of pain will be advised to use only Tylenol and given a week's supply.

Screening visit #2

Return of 3 day food diary

Fasting labs to include- CBC/Diff, ESR, Comprehensive Metabolic Panel, Thyroid Stimulating Hormone, lipid profile, hsCRP, PT/PTT/INR, serum estradiol

Bionutrition consult to review the 3 day food diary and determine subject's "usual diet"

A clinic meal will be provided after labs are drawn.

Dispense Tylenol 325 mg #30, 2 tablets by mouth as needed for pain.

Eligibility will be determined following lab results. Subjects will be scheduled for admission within 1-4 weeks of their screening. If greater than 1 month has passed from screening, safety labs (CBC/DIFF, CMP, PT/PTT/INR) will be re-drawn prior to admission.

Inpatient Admission

Day 0

Admit to RUH at approximately 11 AM

Study diet lunch and dinner

Day 1

Usual diet

Day 2

Spot urine for PGE-M

24 hour urine for testing of the following: PGE-M, estrogen metabolites, creatinine, volume stool sample +/- 1 day

NPO after 9 pm except water

Day 3

Fasting research labs- TNF- α , IL6, IL8, MCP-1, insulin, serum estradiol and estrogen metabolites, serum endocannabinoids

MSKCC labs: CBC, ESR, CMP, hsCRP, PT/PTT/INR, lipid panel, estradiol

Spot urine for PGE-M after completion of 24-hr urine collection

Fat biopsy

Start Celecoxib 200 mg PO BID

NPO after 9 pm except water

Day 4

Bod Pod

Continue Celecoxib 200 mg PO BID

Day 5

Usual diet

Continue Celecoxib 200 mg PO BID

Day 6

Usual diet

Continue Celecoxib 200 mg PO BID

Day 7

Usual diet

Continue Celecoxib 200 mg PO BID

Day 8

Usual diet

Continue Celecoxib 200 mg PO BID

Day 9

Usual diet

Continue Celecoxib 200 mg PO BID

Day 10

Usual diet

Continue Celecoxib 200mgPO BID

Day 11

Usual diet

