Continue Celecoxib 200mg PO BID

Day 12

Spot urine for PGE-M

24 hour urine for testing of the following: PGE-M, estrogen metabolites, creatinine, volume stool specimen +/- 1 day

Continue Celecoxib 200 mg PO BID

NPO after 9 pm except water

Day 13

Celecoxib 200 mg PO in AM

Fasting research lab: TNF- α , IL6, IL8, MCP-1, insulin, serum estradiol and estrogen metabolites, celecoxib level, serum endocannabinoids

MSKCC labs: CBC, ESR, CMP, PT/PTT/INR, hsCRP, lipid panel, estradiol

Spot urine for PGE-M after completion of 24 hour urine collection

Fat biopsy

Usual diet

Discharge from RUH

Dispense Tylenol 325mg #30 tablets.

Upon discharge, tylenol will be provided 325 mg PO #30 (to be taken PRN)

Subjects will be instructed not to take any NSAIDs until their next visit. Tylenol will be provided to reinforce the need to avoid the use of NSAIDs for intercurrent mild discomfort such as intercurrent headaches or influenza-like symptoms and to substitute tylenol. This precaution is taken to prevent distortion of urine PGE-M to be collected 10 days after cessation of Celecoxib administration.

Out-Patient Visit:

End of study visit (7-11 days after discharge)

Spot urine collection for PGE-M

Research labs: serum estradiol and estrogen metabolites, serum endocannabinoids

MSKCC labs: hsCRP, estradiol

Stool collection- Patients will be given a room in the inpatient unit in order to provide a stool specimen at this visit.

Clinic breakfast

For the 5 participants being admitted 2 weeks prior to Celecoxib administration, the inpatient schedule is as follows:

Day 0

Usual diet

Stool sample +/- 1 day

Day 1

Usual diet

Day 2

Usual diet

Day 3

Stool sample +/- 1 day

Usual diet

Day 4

Usual diet

Day 5

Usual diet

Day 6

Usual diet

Day 7

Stool sample +/- 1 day

Usual diet

Day 8

Usual diet

Day 9

Usual diet

Day 10

Usual diet

Day 11

Usual diet

Stool sample (+/- 1 day)

Day 12

Usual diet

Day 13

Spot urine for PGE-M

24 hour urine for testing of the following: PGE-M, estrogen metabolites, creatinine, volume

NPO after 9 pm except water

Usual diet

Day 14

Usual diet

Fasting research labs- TNF- α , IL6, IL8, MCP-1, insulin, serum estradiol and estrogen metabolites, serum endocannabinoids

MSKCC labs: CBC, ESR, CMP, hsCRP, PT/PTT/INR, lipid panel, estradiol

Spot urine for PGE-M after completion of 24-hr urine collection

stool sample +/- 1 day

Fat biopsy

Start Celecoxib 200 mg PO BID

NPO after 9 pm except water

Day 15

Bod Pod

Usual diet

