Continue Celecoxib 200 mg PO BID

Day 16

Usual diet

Continue Celecoxib 200 mg PO BID

Day 17

Usual diet

Continue Celecoxib 200 mg PO BID

Day 18

Usual diet

Continue Celecoxib 200 mg PO BID

Day 19

Usual diet

Continue Celecoxib 200 mg PO BID

Day 20

Usual diet

Continue Celecoxib 200 mg PO BID

Day 21

Usual diet

Continue Celecoxib 200 mg PO BID

Day 22

Usual diet

Continue Celecoxib 200 mg PO BID

Day 23

Spot urine for PGE-M

24 hour urine for testing of the following: PGE-M, estrogen metabolites, creatinine, volume

stool specimen +/- 1 day

Continue Celecoxib 200 mg PO BID

NPO after 9 pm except water

Day 24

Celecoxib 200 mg PO in AM

Fasting research lab: TNF- α , IL6, IL8, MCP-1, insulin, serum estradiol and estrogen metabolites, celecoxib level, serum endocannabinoids

MSKCC labs: CBC, ESR, CMP, PT/PTT/INR, hsCRP, lipid panel, estradiol

Spot urine for PGE-M after completion of 24 hour urine collection

Fat biopsy

Usual diet

Discharge from RUH

Dispense Tylenol 325mg #30 tablets.

Out-Patient Visit:

End of study visit (7-11 days after discharge)

Spot urine collection for PGE-M

Research labs: serum estradiol and estrogen metabolites, serum endocannabinoids

MSKCC labs: hsCRP, estradiol

Stool collection- Patients will be given a room in the inpatient unit in order to provide a stool specimen at this visit.

Clinic breakfast

Methodology for Microbiota Analysis of Stool specimens

Approximately 5 grams of feces will be collected immediately after a bowel movement and rapidly frozen at -80° C.

For each fecal specimen, DNA will be extracted using a phenol-chloroform extraction technique with bead beating for mechanical disruption. The isolated DNA will be purified and then PCR amplified using modified universal primers for the V4-V5 portion of the 16s ribosomal RNA gene. The purified PCR products will be pooled and then barcoded following the Illumina TruSeq Sample Preparation protocol. The library will then be sequenced using the Illumina MiSeq sequencing platform.

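### The Day 14 stool window in the early-admission schedule runs past the first celecoxib dose, so an on-drug specimen can fill the 14-day pre-drug slot

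*Combined protocol and SAP*

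**What the plan says.** Section 12.1 limits the microbiota work to half of the sample: "We additionally plan to study the fecal microbiota of 5 of the 10 participants being studied". Section 12.7 brings these women in 11 days earlier than the others and adds stool collections: "4 additional stool samples will be collected at Days 0,3, 7, and 11, +/- 1 day".

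Their Day 14 list then holds, in this order, blood tests, a spot urine, a further stool with the same allowance ("Stool sample +/- 1 day"), the fat biopsy, and "Start Celecoxib 200 mg PO BID". On Day 15 the entry is "Continue Celecoxib 200 mg PO BID". The next stool is on Day 23, during treatment.

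In the standard schedule the first stool is on Day 2 ("creatinine, volume stool sample +/- 1 day") and celecoxib starts on Day 3.

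The aims that use these samples are in three places:
- Section 12.1 asks whether the microbiota is stable after 3 days, after 7, or only after 14 or longer. It wants to know when collection should "be initiated as a stable baseline before starting the intervention".
- Section 12.2 adds the question whether celecoxib changes the composition.
- Section 12.6 lists time to stability as a secondary outcome.

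**The concern.** A sample meant to describe the microbiota before a drug should not be allowed to come from after the drug has started. The Day 14 window allows this, and the plan has no rule that a specimen must precede the first dose and none on how a later one would be handled.

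Two uses of the sample are exposed. The first is the 14-day point of the stability outcome, where drug exposure would be mixed with time on the study diet. The second is the comparison before and after celecoxib, where a specimen already on drug could stand on the pre-drug side. Only 5 women contribute, so one such specimen is 1/5 = 20% of the women at that time point.

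**Working it through.** The plan gives no figure to reproduce here. The check is a count of days: each stool day plus or minus 1, set against the first-dose day of its schedule. All inputs are from section 12.7.

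| Schedule | Stool day | Allowed days | First dose | Drug status of the allowed days |
|---|---|---|---|---|
| Early admission | 0, 3, 7 | latest is Day 8 | Day 14 | all pre-drug |
| Early admission | 11 | 10, 11, 12 | Day 14 | all pre-drug |
| Early admission | 14 | 13, 14, 15 | Day 14 | 13 pre-drug; 14 depends on the hour; 15 on drug |
| Early admission | 23 | 22, 23, 24 | Day 14 | all on drug |
| Standard | 2 | 1, 2, 3 | Day 3 | 1 and 2 pre-drug; 3 depends on the hour |
| Standard | 12 | 11, 12, 13 | Day 3 | all on drug |

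**Exposure behind a Day 15 stool.** With two doses a day, the most that can precede it is 2 (Day 14) + 2 (Day 15) = 4. The fewest is 1, if only one dose is given on Day 14 and the stool comes before the first dose of Day 15.

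**The two schedules side by side.** Early admission is the standard schedule moved by 11 days, with one exception among these items:
- Baseline 24-hour urine: Day 2 to Day 13, a shift of 11.
- First biopsy and first dose: Day 3 to Day 14, a shift of 11.
- Bod Pod: Day 4 to Day 15, a shift of 11.
- On-treatment stool: Day 12 to Day 23, a shift of 11.
- Last stool listed before treatment: Day 2 to Day 14, a shift of 12.

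The extra day may be deliberate, to obtain a sample at 14 days. Its effect is that a window ending on the start day in the standard schedule runs one full day past it in early admission.

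**The role of the Day 14 stool.** No passage calls it baseline. It is the last stool before the on-treatment one on Day 23. The preceding sample, at Days 10 to 12, is too early for the question about 14 days. Position and aims together make it the last pre-drug sample and the only one near 14 days.

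**Standard schedule.** Only the hours after the first dose on Day 3 are affected; no allowed day is wholly on drug. These women have no other pre-drug stool, but section 12.1 plans microbiota study in only 5 of the 10, so this matters only if their stools are analysed.

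**The case against.** The best reply is that the intended order is already visible. The Day 14 list puts the stool before the biopsy and the first dose, and section 12.1 describes past practice as sampling on a diet like the "pre-study diet and then initiated the intervention". The allowance is attached to every inpatient stool and looks like a practical margin for a specimen that cannot be produced on demand. The women are inpatients, so a late specimen could be recognised. All four of the added samples are drug-free, and the primary outcome does not use stool.

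Most of this stands as context. It does not close the window. List order says nothing about Day 15, which the allowance expressly admits. Where the plan wants a sequence it writes one, as for the spot urine that must follow the 24-hour collection. Section 12.7 describes how stool is collected and frozen but asks for no time record, so a Day 14 specimen passed before the first dose could not be told reliably from one passed after it.

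The reply is also right that the sample's role is inferred. Section 12.1 speaks of past sampling and of guiding future studies, and never mentions the Day 14 stool. The one explicit baseline label for Day 14, in section 12.6, belongs to serum endocannabinoids. Section 12.7 names UniFrac distances between samples but not which pairs will be compared.

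**Conclusion.** The point holds as a minor one. The stated window admits an on-drug specimen at what is, by position and purpose, the last pre-drug stool. One allowed day of three is wholly on drug and one depends on the hour of the first dose, which the plan does not give. The reach is one time point of one secondary outcome and the before/after celecoxib comparison, in 5 women.

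A reader might infer more, and the documents do not support it:
- That the stability result will be biased. Nothing shows that a day of celecoxib changes the microbiota. The abrupt early change cited in section 12.1 followed a change of diet, not this drug. This is an avoidable risk, not a demonstrated bias.
- That a known share of specimens will be late. The count of allowed days is not a probability, and the documents give no basis for one.
- That the plan contradicts its own definition of baseline stool. It has no such definition; the role is inferred.
- That the main result is at risk. The urinary PGE-M analysis is unaffected.

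**What to change.** In section 12.7, with dosing unchanged:

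1. Close the early-admission window at the first dose: Day 13 to Day 14 before the first dose.
2. Record the time of the stool and of the first dose.
3. Keep any later specimen, but classify it as on-drug and do not use it as baseline.
4. If no pre-dose specimen is obtained, let the Day 11 sample serve as the drug-free comparator for the before/after celecoxib question only. Treat that woman's 14-day stability point as missing, because a specimen from Days 10 to 12 cannot answer it.
5. If standard-schedule stools are analysed, apply the same limit to the Day 2 sample: Day 1 to Day 3 before the first dose.

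The cost is a line of schedule wording and two time fields. The downside is a possible missing value: a specimen that would have been accepted late now leaves a gap at 14 days or, in the standard schedule, leaves that woman with no pre-drug stool. A point known to be missing is preferable to an on-drug specimen counted as pre-drug. No specimen is discarded, and sample size and power do not change.
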